All statistical analyses were performed using IBM SPSS Statistics version 26.0. To evaluate baseline homogeneity between the experimental and control groups, independent samples t-tests were used for continuous variables, while chi-square (χ^2) tests or Fisher's exact tests were applied for categorical variables, as appropriate. The effectiveness of the light therapy intervention on sleep quality, fatigue, and emotional distress across time points was assessed using generalized estimating equations (GEE), which account for correlated repeated measures and accommodate missing data. Statistical significance was set at a two-tailed p value of < 0.05 .

Results

A total of 94 participants diagnosed with gynecologic cancer were enrolled and randomly allocated into the experimental and control groups with a 1:1 ratio (47 per group). During the study period, four participants withdrew due to health-related reasons, resulting in a final sample size of 90 (44 in the experimental group and 46 in the control group). The mean age was approximately 52 years. Baseline demographic and clinical characteristics were analyzed to ensure group equivalence. All variables were comparable between groups, except for body mass index (BMI), which showed a statistically significant difference and was adjusted for in subsequent analyses.

Primary and Secondary Outcomes :

Participants completed outcome assessments at baseline and weekly intervals for four weeks following the intervention (T1–T4). Sleep quality was assessed using the

Insomnia Severity Index – Chinese version (ISI-C).Fatigue was evaluated using the Brief Fatigue Inventory – Taiwan version (BFI-T).Emotional distress was measured using the Distress Thermometer (DT).All instruments were administered at baseline (T0), and at days 7 (T1), 14 (T2), 21 (T3), and 28 (T4).

Changes in these outcomes across timepoints and between groups were analyzed using generalized estimating equations (GEE), with BMI included as a covariate to adjust for baseline differences. This model allowed for evaluation of group, time, and interaction effects on outcome measures.

References

Çelik, A., & Usta Yeşilbalkan, Ö. (2023). The Effect of the Bright White Light Application to Cancer Patients Receiving Palliative Care on Their Fatigue Level and Sleep Quality: A Randomized Control Trial. *Omega*, 88(1), 303–317. <https://doi-org.libermg.cgmh.org.tw:8443/10.1177/00302228221093462>

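### With about 90 participants and no small-sample correction named, the joint group-by-time GEE test, if it is the usual robust Wald chi-square on 4 df, runs at about 7% rather than the stated 5%

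*Combined protocol and SAP*

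**What the plan says.** The Statistical Analysis section assesses all three outcomes with "generalized estimating equations (GEE), which account for correlated repeated measures and accommodate missing data". The level follows: "Statistical significance was set at a two-tailed p value of < 0.05". Software is given ("All statistical analyses were performed using IBM SPSS Statistics version 26.0"), but no options are.

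The Results section reports four withdrawals from 94 randomised, "resulting in a final sample size of 90 (44 in the experimental group and 46 in the control group"). Under Primary and Secondary Outcomes, the ISI-C, BFI-T and DT are each taken at T0 and on days 7, 14, 21 and 28, which makes five occasions. The GEE model is fitted "with BMI included as a covariate to adjust for baseline differences", and the text adds: "This model allowed for evaluation of group, time, and interaction effects on outcome measures".

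The document does not state:
- whether the variance is robust or model-based
- the working correlation
- whether time is categorical or linear
- the test statistic and its reference distribution
- any small-sample correction
- which of the three effects decides efficacy

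**The concern.** The robust GEE covariance is itself estimated, here from 90 participants. An uncorrected Wald test refers the statistic to a chi-square, as if that covariance were known, and it also uses a covariance that is biased downward because the divisor is n rather than n − 2. For one parameter the two effects are slight. For a joint test of several parameters they accumulate, because the whole covariance matrix must be estimated and inverted.

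The joint test is the natural one here. T0 is among the five occasions. If it is kept in the model as a response, the group main effect averages in a pre-treatment value and the treatment signal sits in the group-by-time term. With categorical time that term has 5 − 1 = 4 df. If it is tested this way, the declared 5% level is not delivered for any of the three outcomes, and some results with p just under 0.05 would be called significant when they should not be.

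**Working it through.** **Inputs from the document:** level 0.05 two-tailed; n = 44 + 46 = 90; five occasions; BMI as covariate. The plan gives only the nominal 5%, so there is no figure for the true size to reproduce.

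**Assumptions, not in the document:** robust Wald statistic W compared with chi-square; categorical time, so q = 4.

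**1. Analytic size of the joint test.** With complete data and two groups, W = [n/(n − 2)] × T², where T² is Hotelling's statistic on 88 df and T² × 85/(4 × 88) follows F(4,85).
- The chi-square(4) 95% point is 9.488.
- On the F scale this is 9.488 × (88/90) × 85/(4 × 88) = 2.240.
- P(F(4,85) > 2.240) = 0.071.
- With all 94 randomised (92 and 89 df): P(F(4,89) > 2.246) = 0.070.

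**2. One degree of freedom** (single time-point contrast, or linear time): 1.960 × √(88/90) = 1.938, and P(|t88| > 1.938) = 0.056. Simulated single contrasts gave 5.4% to 5.7%.

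**3. Simulation of the joint test under no group-by-time effect.** Each scenario used 44 and 46 participants, five visits, BMI in the model and 20,000 runs (Monte Carlo standard error about 0.2 points).

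| Working correlation | Data | Robust Wald, chi-square(4) | Hotelling-type F(4,85) |
|---|---|---|---|
| Independence | AR(1) | 7.2% | 5.1% |
| Exchangeable | AR(1) | 7.1% | 5.1% |
| Exchangeable | Exchangeable | 7.2% | 5.1% |
| Exchangeable | AR(1), skewed | 6.7% | 4.4% |
| Exchangeable | AR(1), rounded 0–10 scale | 7.1% | 5.0% |
| Exchangeable | AR(1), 5% of visits missing | 7.3% | 5.2% |

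A separate run without BMI (40,000 trials per structure, complete data) gave 7.0% under both exchangeable 0.5 and AR(1) 0.7.

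**4. Model-based variance instead of robust, 4 df:** 5.9% when the exchangeable working correlation is right, 7.4% with exchangeable working correlation and AR(1) data, 1.1% with independence working correlation and AR(1) data.

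**5. Which corrections restore 5%?** The F(4,85) 95% point is 2.479, and 4 × 2.479 = 9.916.
- *W/4 against F(4,85), covariance uncorrected:* 9.916 × (88/90) × 85/352 = 2.341, tail 0.061; simulated 6.0%.
- *Divisor corrected to n − 2, then F(4,85):* 9.916 × 85/352 = 2.395, tail 0.057; simulated 5.5%.
- *Mancl-DeRouen covariance, then F(4,85):* with about 45 per group the covariance grows by about (45/44)². The point becomes 9.916 × (45/44)² × (88/90) × 85/352 = 2.449, tail 0.052; simulated 5.0% to 5.1%.
- *Hotelling-type rescaling:* W × (88/90) × 85/(4 × 88) = W × 85/360, referred to F(4,85). This is exact under the model in step 1 (5.0%); simulated 4.9% without BMI, and as tabulated with BMI.

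**6. Effect on a reported p-value.** The correct critical value for W is 2.479 × 360/85 = 10.50. The chi-square(4) tail beyond 10.50 is 0.033. Uncorrected p-values between about 0.033 and 0.05 are therefore the ones at risk.

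**The case against.** The strongest reply is that the 7% belongs to one branch of an under-specified plan. The document names neither a robust Wald chi-square nor categorical time, and it does not say that the interaction decides efficacy. Other readings give other answers. Linear time or separate contrasts are off by only about 0.6 points. A model-based Wald test can be conservative or liberal. A robust score test of the same 4-df hypothesis would hold its level (4.8% analytic, 4.7% simulated). The sample size of 78 also fits a between-groups test: it is reproduced, with power 0.804, by a five-measure repeated-measures F test with an assumed within-person correlation of 0.5. The planners may therefore have had a 1-df group effect in mind. Finally, ordinary GEE with 90 participants is a conventional choice.

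The reply about silence stands, and it is why the figure must be stated conditionally. It does not remove the point. The robust Wald test is what plain GEE usually means, and an assessment by time point fits categorical time. The model-based alternative keeps its level only if the unstated working correlation suits the data, and even then it gave 5.9%. The reply about convention bears on how much this matters, not on whether the level is met.

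A reader might also infer that the excess compounds over three outcomes into a large overall false-positive rate. The documents do not support that. Such a calculation treats three self-reported scores from the same patients as independent, and most of the resulting figure would come from testing three outcomes without adjustment, which is a separate matter.

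**Conclusion.** The point holds in conditional form and is minor. Given a robust Wald chi-square and categorical time, the joint group-by-time test has a true error rate of about 7% instead of 5% for each outcome. That is roughly 2 percentage points too high, and it was stable across the correlation structures, outcome distributions and missingness examined. For 1-df tests the rate is about 5.6%, which is of little consequence.

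A reader might conclude that the trial's efficacy test is known to run at 7%. That goes too far, because the variance estimator, the time coding and the deciding effect are inferred rather than written. What can be said is that the plan does not secure its stated level, that the most usual reading misses it, and that a simple correction would meet it. Although the document is partly in the past tense, it reports no treatment-effect results, so no conclusion in it is overturned.

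**What to change.** In Statistical Analysis, and consistently under Primary and Secondary Outcomes, state that time is categorical, and name the variance estimator, the working correlation and the effect that decides efficacy. Then specify one of the following for the joint group-by-time test:

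- a bias-corrected robust covariance (for example Mancl-DeRouen) with an F(4, about 85) reference; size about 5.0% to 5.2%
- the Hotelling-type rescaled statistic W × ((n − 2)/n) × 85/(4 × 88), referred to F(4,85); size about 5.0%. With n = 90 this is W × 85/360, so it needs only the ordinary robust Wald statistic.

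For single time-point contrasts, use bias-corrected standard errors and t rather than z. Do not simply divide the uncorrected statistic by 4 and look up F(4,85), since that leaves the size at about 6.0% to 6.1%.

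The cost is a few sentences, a rerun of the tests on the existing data, and slightly larger p-values. No new data are needed.
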